- Both of the programs include 14 sessions with one session to be covered each week. Most moms spend between 40-60 minutes each week using the iPhone to work on the program and you can start and stop as needed. It will save your place. Each mom will be assigned an individual coach who will provide support through a video call each week. The call will involve watching a video that was created during the session. Each call will last about 20-30 minutes.
- Participants will be asked to complete 4 remote assessment calls: 2 assessment calls at the beginning of the project and 2 assessment calls at the end. Each assessment call will last about 1 hour. On those calls, we will make a video of you and your baby playing together and looking at books. We will also complete some online questionnaires that asks questions about you and your baby.
- Once you complete the assessment calls, we will schedule one more call to show you how to use our app on the iPhone. This call will last about 1 hour. Then you will begin completing sessions on your own with the support of your coach.
- There may be some benefits to mothers who participate in the program.
 - You may find that answering questions about parenting your baby is helpful and interesting.
 - You will have the iPhone with free data, texting, and calls to use during the study.
 - You will be able to keep the iPhone upon completion of the study. Although we will not continue to pay for phone service, you can use the phone through wireless Internet if you have access to it.
 - You will have the videos on the iPhone that you created during on the program.
 - You will be helping researchers to learn whether the program you receive is helpful for mothers of infants.
- There are few risks to being in the program.
 - You may feel uncomfortable answering some of the questions asked today or during the project. You can stop this call at any time and skip any questions during the project that you do not want to answer.
 - All information we collect is stored in a secure, locked office or database that is only accessible by approved research staff. We will use a study number rather than your name on all study records. There is only one code sheet use to identify research participants and it is stored securely in a password-protected file on a locked computer in a locked office.
- If you have any concerns or complaints, you can find IRB contact information at gsu.edu/irb

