- Can we leave a message at this number? If it's a cell # - ask if you can text her appointment reminders.*
- If for some reason I can't get a hold of you, it would be helpful to have some contact names and numbers of people who would be able to reach you. Do you have one or two people who typically stay in touch with you and know how to locate you even if you move or change numbers? Can I get their names and phone numbers?*

- Record the contact names/numbers on the recruitment form

Recap:

- *I believe I have all the information I need. I'd like to quickly recap a couple of points*
 - I will email and mail you the consent form and iPhone agreement.
 - On our scheduled call, we will go over the forms and I will answer any questions you have. It will take about 20 minutes.
 - Then we will go over the next steps of sending the iPhone and setting up the next calls.
- *Do you have any questions about the project in general?*
 - If yes, try and answer any questions they have or let them know you will call back with the answer.
 - If no, continue.
- *Give us a call if you have any questions or concerns before your scheduled appointment. We will also give you a reminder call or text the day before your appointment.*
- *We really want to thank you for your interest in our study and being willing to let us come to your home during this busy time in your life. We look forward to meeting with you on _____ at _____ am/pm.*

❖ **CONTINUE TO 'AFTER THE INITIAL RECRUITMENT CALL' STEPS (page 9)**

6. **PARTICIPANT IS ELIGIBLE – WAITLIST**

Based on the information you just gave me, you are eligible to participate in the program at this time.

Explain Waitlist: *We currently have as many moms as we can take in the program right now but we will have openings soon. We estimate that you will be able to enroll in about [give approximate timeframe, i.e. 2 weeks, 1 month, etc.]. Since we already know you are eligible we will simply need to schedule the first **call** as soon as we have an opening. I will call back to schedule as soon as I know there's a spot. If I can't reach you within a week, I will have to move to the next person on the waitlist.*

What questions do you have right now? Answer any questions.

Let me confirm all of your contact information so we can be sure to reach you.

Confirm all the contact and demographic information. Unless they refuse, get at least 2 phone numbers:

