- **NOTE:** Make sure to confirm if mailing address and physical address are different, confirm spelling of first and last name, and confirm date of birth and name of baby
- *Is this the best number to call to follow-up with you?*
- *Can we leave a message at this number? If it's a cell # - ask if you can text her appointment reminders.*
- *If for some reason I can't get a hold of you, it would be helpful to have some contact names and numbers of people who would be able to reach you. Do you have one or two people who typically stay in touch with you and know how to locate you even if you move or change numbers? Can I get their names and phone numbers?*
 - Record the contact names/numbers on the recruitment form

Recap:

- *I believe I have all the information I need.*
- *Give us a call if you have any questions or concerns before you hear from me again.*
- *We really want to thank you for your interest in our study and for your patience while we wait for a spot to open up.*

When you call mom back to schedule appointment, use scheduling script in section 5.

❖ CONTINUE TO ‘AFTER THE INITIAL RECRUITMENT CALL’ STEPS (page 9)

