7. AFTER THE INITIAL RECRUITMENT CALL

[figure not shown]
- Update Access Database - Tracking Information Form
 - Update/confirm contact, alternate contact, and demographic information
 - Enter phone screen information
 - Enter eligibility information
 - Enter Call Attempt information and enter Call Back Date if needed to call back to schedule preassessment

- If applicable, enter Scheduled Appointments information

Scheduled Appointments						
Mom ID	Type	Date	Appointment Details			Check the Completed Assessments Q1 Q2 Interactions iPhoneTrain Notes
			Time	Assessor	Status	

- Update Matriculation Table
 - Entire 'Screening' section
 - 'PreAssessment Scheduled' column of 'PreAssessment' section (if scheduled)

- Update Google calendar
 - Add scheduled preassessment on Assessment Visit calendar
 - Add assessor as 'guest' when known

Preassessment ID ###

Mar 21, 2018 10:00am to 12:00pm Mar 21, 2018 TIME ZONE

All day Does not repeat

EVENT DETAILS FIND A TIME

Add location

Add conferencing

ADD NOTIFICATION

Assessment Visit

Busy Default visibility

Add description

[contact]

GUESTS

Gucata can:

Modify event

Invite others

See guest list

Mom & Baby Net Remote Assessment & Training Procedures

Schedule Consent Call (10 minutes) [PROJECT COORDINATOR]

1. Explain changes in procedures (moms on wait list)
 - a. *Hi! This is [name] with the Mom & Baby Net project. Do you have about 10 minutes to talk? I was calling to let you know that we have a spot open for you in the project but our procedures will be a little different since we cannot do home visits right now. Are you still interested in participating and hearing what the next steps will be?*
 - i. If no: *I'm sorry to hear that. Can I ask why you are no longer interested?* If mom is too overwhelmed right now, offer to leave her on the waitlist and check back again when the next spots are open.
 - ii. If yes: continue with script
 - b. *Great! If you remember, the usual next step would have been to do the first home visit, but due to coronavirus, we are not doing home visits. Instead, we will do everything via phone or video call. We will walk you through each step along the way. After this call, you will be in touch with your coach, who you will be working with you for the rest of the program.*
2. Explain sending consent and iPhone agreement

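### The remote waitlist script puts mothers who meet the trial's depression criterion on an open-ended wait without advice to see a doctor, a resource list or a crisis line

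*Protocol*

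**What the plan says.** The relevant text is in Protocol section VI, Remote Recruitment Call, part 6 (Participant is Eligible – Waitlist). Staff reach it from the Depression Screening step when the mother is eligible and a waitlist is active. To be eligible she needs a PHQ2 of 3 or more on the call or, if already screened, a qualifying score. The Recruitment Form accepts PHQ9 of 10 or more, PHQ2 of 3 or more, or Edinburgh of 11 or more.

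The script opens with "We currently have as many moms as we can take in the program right now but we will have openings soon". Staff then fill in an expected wait, with the prompt "give approximate timeframe, i.e. 2 weeks, 1 month, etc". If she cannot be reached within a week when a place opens, she is told, "I will have to move to the next person on the waitlist". Contact details are confirmed, and the closing offer is "Give us a call if you have any questions or concerns before you hear from me again". The after-call steps are database, tracking-table and calendar entries. For the later call-back the instruction is "When you call mom back to schedule appointment, use scheduling script in section 5".

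A separate script, Schedule Consent Call in the Remote Assessment & Training Procedures, covers mothers already on a wait list. For one who declines it says: "If mom is too overwhelmed right now, offer to leave her on the waitlist and check back again when the next spots are open".

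**The concern.** Staff who follow the waitlist script exactly tell a mother with a positive depression screen that the program is full, and give her nowhere to turn meanwhile except the study team. Yet part 4 of the same call gives a mother who screens negative conditional advice to see a doctor or community program.

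What is at stake is participant safety before consent. No endpoint or analysis is affected. The gap matters most for mothers with no provider screen. Some sites refer without screening (Referrals from sites), and mothers may find the website themselves (Online Referrals/Interest). On the visible text, their only screen before the wait is the PHQ2, whose two questions do not ask about self-harm.

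**Working it through.** The documents give no figure to reproduce and no calculation applies. The check is to read each script for three items (advice to see a doctor or community program, a resource list, a crisis line) and note when the next contact comes.

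| Script (Protocol) | Doctor or program advice | Resource list | Crisis line | Next contact |
|---|---|---|---|---|
| Remote call, part 4: screens below threshold | Yes, if things change | No | No | None; she may get back in touch |
| Remote call, part 5: eligible, no waitlist | No | No | No | Call in 4–5 days |
| Remote call, part 6: eligible, waitlist | No | No | No | When a place opens; examples 2 weeks, 1 month; no maximum |
| In-person call, part 5: eligible | No | No | No | Home visit scheduled on the call; interval not stated |
| Schedule Consent Call: declines as overwhelmed | No | No | No | When places next open; no time given |
| Community events: not eligible | No | Yes | No | None; she may contact the team |

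The waitlist script and its after-call steps contain 0 of the 3 items. So do the other two scripts for eligible mothers. Omission alone therefore does not single out the waitlist; omission combined with an open-ended delay does. The only indirect limit on the wait is that the baby must be under 12 months at first assessment.

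Next, when does the trial's own support reach her on the remote route?

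- **Handbook and phone.** The handbook holds the Georgia Resources section (Referrals from community events), and the phone is loaded with crisis numbers (iPhone Customization Questionnaire). Both are described at the Consent Call and sent only after staff confirm the signed pages (After Consent Call, item 5).
- **Self-harm questions.** PHQ9 item 9 and ATQ item 6 are checked at the Pre-Assessment Call, after the materials arrive.
- **Self-harm decision tree** (section IV). Its entry condition is one of those two items or a spontaneous report. Before consent, only the spontaneous report can apply.
- **Adverse event recording** (section V). It starts when the consent form is signed, so events during the wait fall outside it.

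All four lines of support therefore either start after consent or, before it, depend on the mother raising self-harm herself.

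**The case against.** The strongest reply is that the visible pattern is consistent: resources come at assessment, for enrolled mothers, and no call script for eligible mothers offers them earlier. That stands, and it narrows the point to the delay. A gap of 4 to 5 days before the next call is different from a wait without a stated limit.

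There is partial mitigation. Some site-referred mothers have a home visitor, who goes through the parent letter with them. Staff answer questions and invite calls. The decision tree covers self-harm thoughts that a mother volunteers. The parent letter, website text and consent form may contain advice but cannot be seen, so the point is limited to the phone scripts.

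Four stronger readings are tempting and are not supported:

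- *Every waitlisted mother has just screened positive.* That holds only when the PHQ2 is asked on the call. Provider-screened and website mothers met the criterion earlier.
- *The days until materials arrive or self-harm is checked can be counted.* The waits are placeholder examples, and delivery and handling times are not fully stated. It is also unclear whether the quoted wait ends at the call-back or at consent.
- *One mother could be waitlisted and then sent back to the list as overwhelmed.* The call-back goes to part 5, and remote callers have already heard "Participants will be asked to complete 4 remote assessment calls". The Schedule Consent Call tells its mothers that "the usual next step would have been to do the first home visit", so it may be a changeover script for a different group.
- *Being overwhelmed is a clinical signal.* In that script it is a reason for declining a study place, so this branch is the weaker case.

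**Conclusion.** The point holds as a low-cost safety improvement. A script reached only by mothers meeting a depression criterion starts an open-ended wait and includes none of three simple forms of help-seeking advice. The same call gives one of them, conditionally, to mothers who screen negative.

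Its size cannot be stated beyond that. The documents do not give the number waitlisted, the actual waits or the share with a provider contact, and nothing shows that harm occurred. This is a gap in the scripts, not a contradiction between documents. The conclusion assumes that staff follow the scripts as written and that the unseen materials do not already supply the advice to these mothers.

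**What to change.** In part 6 of the Remote Recruitment Call, add:

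1. An unconditional form of the part 4 advice, encouraging her to talk to her doctor or a local community program now.
2. An offer of the existing Georgia Resources list.
3. The two crisis line numbers from the Crisis Help Card. Give the numbers and not the unedited card, because its non-emergency row sends her to a coach she does not yet have.

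As an optional second step, use the same line when a mother declines in the Schedule Consent Call because she is overwhelmed. It could equally go into the other scripts for eligible mothers. Exact wording is for the sponsor's clinicians. If recruitment is over, the change applies to any reuse of the manual.

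The cost is a line or two per script, from materials the trial already holds. The downside is that some mothers may start other care and be less depressed at baseline. On the remote route this precedes randomisation (After Consent Call, item 4), so it is balanced across arms in expectation. The SAP (Analytic Strategy, Constructs) already plans to examine other treatment, including medication, as a potential moderator.

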7. AFTER THE INITIAL RECRUITMENT CALL

[figure not shown]
- Update Access Database - Tracking Information Form
 - Update/confirm contact, alternate contact, and demographic information
 - Enter phone screen information
 - Enter eligibility information
 - Enter Call Attempt information and enter Call Back Date if needed to call back to schedule preassessment

- If applicable, enter Scheduled Appointments information

Scheduled Appointments						
Mom ID	Type	Date	Appointment Details			Check the Completed Assessments Q1 Q2 Interactions iPhoneTrain Notes
			Time	Assessor	Status	

- Update Matriculation Table
 - Entire 'Screening' section
 - 'PreAssessment Scheduled' column of 'PreAssessment' section (if scheduled)

- Update Google calendar
 - Add scheduled preassessment on Assessment Visit calendar
 - Add assessor as 'guest' when known

Preassessment ID ###

Mar 21, 2018 10:00am to 12:00pm Mar 21, 2018 TIME ZONE

All day Does not repeat

EVENT DETAILS FIND A TIME

Add location

Add conferencing

ADD NOTIFICATION

Assessment Visit

Busy Default visibility

Add description

[contact]

GUESTS

Gucata can:

Modify event

Invite others

See guest list

Mom & Baby Net Remote Assessment & Training Procedures

Schedule Consent Call (10 minutes) [PROJECT COORDINATOR]

1. Explain changes in procedures (moms on wait list)
 - a. *Hi! This is [name] with the Mom & Baby Net project. Do you have about 10 minutes to talk? I was calling to let you know that we have a spot open for you in the project but our procedures will be a little different since we cannot do home visits right now. Are you still interested in participating and hearing what the next steps will be?*
 - i. If no: *I'm sorry to hear that. Can I ask why you are no longer interested?* If mom is too overwhelmed right now, offer to leave her on the waitlist and check back again when the next spots are open.
 - ii. If yes: continue with script
 - b. *Great! If you remember, the usual next step would have been to do the first home visit, but due to coronavirus, we are not doing home visits. Instead, we will do everything via phone or video call. We will walk you through each step along the way. After this call, you will be in touch with your coach, who you will be working with you for the rest of the program.*
2. Explain sending consent and iPhone agreement
 - a. *I will email you a copy of the project's consent form. This document will explain in detail the purpose of the Mom and Baby Net project, what you will be doing in the project, and how we will keep your information safe. We are taking necessary precautions to keep you, your family, and our staff healthy during the Coronavirus pandemic. The Pre-assessment and training visits will be conducted remotely using Zoom – an app that allows us to have a video call. I will later explain how Zoom works if you choose to participate.*
 - b. *The iPhone agreement form will also be emailed to you. This document covers expectations of loaning you the iPhone to complete the Mom and Baby Net project. Your phone service will be covered while you are participating in the program. We will monitor your progress on a month to month basis. If you are making progress and staying in communication with your coach, we will renew your service for the next month. If we lose contact with you, or you are not making progress in the program, your phone service may be discontinued; If we cannot reach you and your phone is not returned, it will be reported as lost or stolen.*
 - c. *I will also mail a copy of both of these forms to your home. Have you still been receiving mail and packages as usual during this time?*
 - d. *What questions do you have? [answer any questions]*
 - e. *The next step is to schedule a call to talk about the Consent and iPhone agreement forms after you receive them in the mail. You will do this call with your Coach, who will be with you for the rest of the program. She will go over both of these forms, answer any questions you have, and explain the next step which will be sending the iPhone and materials to you. Please think about a time where you will be able to talk for about 15 minutes and she will reach out tomorrow to schedule that call.*

3. Confirm email and mailing address

After Consent Scheduling Call

1. Assign participant ID and enter into Access
2. Notify coach ASAP to reach out to participant to schedule consent call.
3. Mail & email Consent and iPhone agreement
 - a. Note to add in email/envelope: We will review these documents on our next call. After all your questions are answered, you will sign them, take a picture of each signature page, and will text them to the project staff member who you speak with on that call.

Day Before Consent Call

1. Call or text mom to confirm she received the consent & iPhone agreement in the mail
2. Confirm time of call for next day
 - a. Reschedule if necessary (update Access and Matriculation table)

Consent Call (20 minutes) [ASSIGNED COACH]

1. Review consent the same as you would at a home pre-assessment (mom looking along on own copy)
2. Review iPhone agreement the same as you would at a home training visit (mom looking along on own copy)
3. *What other questions do you have about either of these documents or the program?* [answer questions]
4. *Are you still interested in participating?*
 1. If yes: *Great! Please go ahead and sign both pages. As soon as we get off the phone, take a picture of every page (even those that don't have a signature) and text them to the number I am calling from ####-####-####.*
 2. If no: *I am sorry to hear that. Can I ask why you changed your mind?*
5. Explain drop off or mailing of phone/accessories/manual
 1. *The next step is to drop off or mail your iPhone, accessories, and materials. We will sanitize all materials before getting them to you. In the bag you will find two baby books, your Mom and Baby Net handbook, iPhone, charger, headphones, and a tripod stand. Inside your Mom and Baby Net handbook in the front pocket of the binder, you will find a card with information about how to connect on Zoom.*
 2. If dropping off (if they have experienced issues getting UPS packages, this will be the best option): *To minimize contact and keep with social distancing, I will call once I have arrived outside and parked. I will remain on the phone with you, place your bag at the door, and let you know when to retrieve it. While you are on the phone, we will select a time for us to have our next call.*
 3. If mailing: *I will track the package and call or text to confirm it has arrived.*
6. Explain Zoom Training & Preassessment calls

1. *After you receive everything, we will have another call. We will connect via Zoom video chat and you will get an instruction card for that in your materials. Once you are familiar using Zoom, that's how we will communicate for the rest of the program. Also, on that call, we will record 2 5-minute videos of you and [baby's name] playing together and looking at some books that we will send. We will also begin the surveys, which are split into 2 parts. We will likely not finish everything on one call, so we will go ahead and schedule 2 separate calls for the same week.*
7. Ask mom some questions to determine the best time and way to complete the pre assessment remotely

 1. *Do you have laptop or tablet that is on data and/or wifi?*

 - i. If yes: *Great – if you would like, you can use your laptop/tablet to do the surveys. You can connect to Zoom on the project iPhone.*
 - ii. If no: *That is fine – you will be able to use the project iPhone to complete everything.*
 2. *The videos need to be created away from other people so that the interaction will not be interrupted by other people in the home; The video will need to be created away from sources of noises that could be picked up on the camera's microphone (like a noisy kitchen, television, or street). Where do you think the best place will be in your home to make the video?*
 3. Ask questions to help mom determine when would be the best time to do the call to record videos and complete the surveys. Some moms may know exactly when a good time is while others may need to think through some of these questions to figure it out. The purpose of these is to prime mothers for a successful video capture call.

 - i. *We want to make sure that we schedule the call at a time when your baby has been recently fed, is not sleepy and is feeling well AND when your other children are busy doing something fun that they like to do.*
 - ii. If there are other children in the home: *Was there a time yesterday when your older children were busy doing something that they were having fun with? What was it?* If it was appropriate, find out the details so you can encourage it for the call. If it is not appropriate or feasible, then help her think of something that is (i.e. watching an appropriate movie/show, playing a game). *When did they do that? Where? How long?* If the mother identifies something realistic and doable, encourage her to do that and have her set the specific reminder on her phone to get the other kids set up doing that activity 15 minutes BEFORE your scheduled call.
8. After working through these questions, schedule 2 1-hour sessions on different days, as close together as schedules allow (e.g., Wednesday & Thursday or Wednesday & Friday) with the mom to complete the pre assessment procedures. They should be 4-5 days after you drop off box of materials at UPS.

 1. Ask the mother to schedule the appointment times in her phone and show you:

 - i. 15 min before Call 1: Activity for other children
 - ii. Time of Part I Call (videos & Part 2 Qs)
 - iii. 15 min before Call 2: Activity for other children
 - iv. Time of Part II Call (Part 1 Qs)

9. Confirm shipping address (for UPS packages) or physical address (if dropping off materials)
10. iPhone Customization Form
 1. *The last information we need from you is to set up your iPhone before we send it. We will create an Apple ID for the phone and you will get the password for that once you finish the program. That means you will not be able to add apps once you get the phone. We have to control the space on the phone to make sure there is enough space for our app to run smoothly while you are in the program. I am texting you a link to an online form where you can choose up to 10 apps to have on the phone. We will add those when we set it up.*
 2. Text mom link to iPhone customization form: [link & add to preassessment links page]
11. Wrap up & signature reminder
 1. *Do you have any final questions? [answer questions]. We are excited to have you in the program and thank you for your patience. Remember to sign the consent form and iPhone agreement and send me a photo of every page as soon as we get off the phone and complete the iPhone customization form using the link. Once we have that, we will get the phone and materials ready to send to you.*

After Consent Call

1. In Access, add appointment(s) as 'scheduled' for pre assessment (enter both dates and times on separate lines)
2. In Matriculation Table, list scheduled pre assessment date
3. Let Assessment Coordinator know as soon as participant texts Consent and iPhone Agreement (all pages, not just signature page). Assessment Coordinator will set up iPhone.
4. Prior to iPhone set up, the Intervention Project Coordinator implements randomization procedures. Using a random number generator, mother-infant dyads were randomized, in a 1:1 allocation, to one of the two parallel interventions: Mom and Baby Net or Depression and Developmental Awareness. The Intervention Project Coordinator notifies the PI to review condition assignment and assigns case to intervention coach.
5. Drop off/mail materials (Assessment Coordinator)
 2. Prior to dropping off bag to participant or box to UPS, confirm that mom texted signature pages.
 3. Drop off sanitized iPhone w/ case + headphones + charger + tripod + program handbook (make sure Zoom instruction card is in inside pocket) + books + welcome letter
 4. When you receive email confirmation that box has been delivered, call or text mom to confirm that she received everything.

Day Before Pre-Assessment Call

1. Send mom a reminder via text or call
 - a. Remind her of time for scheduled call
 - b. Remind her that the videos need to be created:
 - i. At time when your baby has been recently fed, is not sleepy and is feeling well
 - ii. Away from other people so that the interaction will not be interrupted by other people in the home;
 - iii. Away from sources of noises that could be picked up on the camera's microphone (like a noisy kitchen, television, or street)

- c. Remind her, if applicable, of the fun activity for her older children, which they are going to get set up before the call with you
- d. Confirm that she has all the project materials that were sent to her & that her phone will be charged to at least 50% for the call. She will want to have headphones to use for the surveys unless it is just her and the baby in the home.

Pre-Assessment Call: Videos & Questionnaires [Assigned Coach]

(Split into 2 calls, 1 hour each; schedule 2 days as close together as possible)

1. Prior to getting on call
 - a. Gather needed paperwork (or go to electronic versions on Dropbox -> MomAndBabyNetNIHR01 -> Assessment -> Assessment Protocols & Forms -> Remote Assessments
 - i. ASRI
 - ii. Data checklist
 - iii. PDFs of surveys
 - iv. If mom is using a laptop/tablet to complete the surveys, have an email prepped with the link to send her. Do not send the day before.
2. Start Zoom call and greet mom as you normally would.
3. Zoom & iPhone orientation
 - a. Make sure mom is familiar with Zoom and troubleshoot if she has any issues with audio, video, etc.
 - b. Ask mom if she's ever used an iPhone before.
 - i. If not, give her a brief tutorial (turning off and on; answering phone; sending texts; Safari browsing; opening and closing apps; taking screenshots). Reference handbook section that covers this.
 - ii. Show mom all of the contacts that you added to her phone and explain the method for entering them (e.g., DR Smith Pediatrician; MED Poison Control). Reference handbook section that covers this.
 - iii. Show mom how to add numbers to Favorites (coach has already been added to favorites).
4. Review what you will be doing for the assessment part of the project
 - a. *For the pre assessment, we will record 2 5-minute videos of you and your baby – one of you playing together and one of you looking at the two books we included in your box of program materials. You will answer some questions on a survey I will send the link to. It is split up into 2 parts so we will probably not complete everything today, which is why we scheduled 2 times to meet. Also, it's important for you to understand that this will be very different from the actual program – it will be a little more tedious and less interactive, but then we will get to the app program, which will be more interactive and informative!*
5. Assessment Videos
 - a. *First, we will record the two videos.*

b. Setting up for videos

- i. Before beginning video protocol, ask the mother if she began the activity for other children as planned. Praise her successful action if she has done this already. If she has not done this, let her know that you want her to do this now. Help her with suggestions if needed.
- ii. Prepare for Video Recordings
 1. Remind the mom that it's important that baby is feeling well, is not hungry, and is not sleepy. If hungry, mom needs to feed baby first. If baby is sleepy or not feeling well, the videos can be captured during the next call. Proceed to complete questionnaires (get both done if possible).
 2. Let mom know that we need a relatively quiet place with plenty of light. Remind her of the location she identified and that
 - a. The space should be away from others so that the interactions will not be interrupted by other people in the home
 - b. If possible, pick a room away from sources of noises that could be picked up on the camera's microphone (like a noisy kitchen, television, or street)
 3. Guide mom on how to set up the phone for the videos
 - a. Landscape view (horizontal)
 - b. Can view enough area to have mom & baby in screen
 - c. Confirm there is enough light (not in front of a window)
 - d. Make sure the television/music is off (no background noise)
 4. Tips and Troubleshooting
 - a. Coach should not talk during video recording.
 - b. If mom asks you to stop recording video or if mom needs to leave the room, pause the recording until mom is ready to resume.

c. Free Play Video

- i. Record Free Play Instructions
 1. Select record on Zoom
 2. *Let's get started with the first part of the video by spending five minutes with you and your baby doing something that you enjoy doing together.*
 3. *What I'm interested in seeing are things that you and your baby are both comfortable with and used to, and things that your baby loves to do.*
 4. *Please feel free to move around as is comfortable for you and your baby but make sure that both you and your baby are visible on the screen at all times.*
 5. *Attend to any needs your baby might have during this time just as you normally would.*
 6. *After these 5 minutes, I will stop recording then I will give you the instructions for the second part of the recording which lasts 5 minutes. What questions do you have?*

7. Answer any questions mom has.
8. Stop recording on Zoom.

- ii. Record Free Play Video
 1. Give mom time to finish setting up for the video and confirm that she is ready.
 2. Coach should record using Speaker View and have the running time visible (or use a timer on your phone) set to make sure you get a minimum of 5:30 minutes of recording.
 3. *I am going to start recording, say an intro sentence for the video, then ask you to begin.*
 4. Select 'record' on Zoom
 5. *This is an interaction video with participant [say ID #], the mother's initials are [say mom's initials]*
 6. To mom: *You can begin now.* Coach – mute your microphone to mute your own background noise.
 7. After 5:30 minutes, stop recording on Zoom, unmute yourself, and say *Ok, the first video is finished.* Allow the mom to transition. *Now we will do the second video.*

- d. Books video (use Color and Animal baby books given to all moms)
 - i. Record Book video instructions
 1. Select record on Zoom
 2. *During the next five minutes, you and your baby can spend a little time with these books.*
 3. *However you want to use the books with your baby is fine.*
 4. *Feel free to attend to whatever needs your baby might have.*
 5. *What questions do you have?*
 6. Answer any questions mom has.
 7. Stop recording on Zoom.
 - ii. Record Books Video
 1. Give mom time to finish setting up for the video and confirm that she is ready.
 2. Coach should record using Speaker View and have the running time visible (or use a timer on your phone) set to make sure you get a minimum of 5:30 minutes of recording.
 3. *I am going to start recording, say an intro sentence for the video, then tell you to begin.*
 4. Select 'record' on Zoom
 5. *This is an interaction video with participant [say ID #], the mother's initials are [say mom's initials]*
 6. To mom: *You can begin now.* Coach – mute your microphone to mute your own background noise.
 7. After 5:30 minutes, stop recording on Zoom, unmute yourself, and say *Ok, the second video is finished.*

- e. Reset Zoom

- i. *Great job on the videos! Now we can continue to the surveys. So we don't run out of time, I am going to end this call and we are going to get right back on this same Zoom to continue.*
- ii. End Zoom call then start again immediately.
- iii. Ask mom if she needs to take care of any needs for the baby or if she is able to put the baby down or give to another adult so she can focus on the surveys.

6. Questionnaires

- a. Pre Assessment Questionnaire Part 1 (labeled as part 2 in Qualtrics: T1_part2)
 - i. *Now we will begin the questionnaires. They are split into two parts, so we don't have to complete both today. Each part will take 30-40 minutes to complete. We can start Part 1 and see how far we get. If we need to, we can complete the rest of the survey on our next scheduled call.*
 - ii. *I am now sending you a link to the first survey we will complete. Please let me know when you have received it and you can go ahead and click on it.*
 - iii. Send link to T1_Part 2 survey to mom
 - 1. Link: (see links document)
 - 2. If mom is doing surveys on their phone, text survey link to mom's project phone
 - 3. If mom is using laptop, email survey link
 - 4. If mom is restarting a partially finished survey, see steps below to get link to that survey and start where she left off
 - iv. Coach will have PDF of survey open to look at (printed or on computer). If mom needs to stop before reaching the end of this survey, make a note on the PDF of where she ended.
 - v. Set up surveys
 - 1. If mom is using their project phone: *When you click on the link, we will stay on Zoom. Even though we won't be looking right at each other through video, I will walk you through everything.*
 - 2. If mom is using own laptop/table: *If you want to set your phone up somewhere during these surveys, we will not necessarily need to see each other, but I will be walking you through each section of the survey.*
 - vi. Coach will instruct mom how to fill out the first page of info: ID #, mom initials, assessor name, date (mm/dd/yyyy)
 - vii. Read instructions for each section
 - 1. Coach will read through introductory instructions and instructions for first section.
